A 3 + 3 dose-escalation scheme will be implemented and dose intervals will follow those outlined in Section 6.4. Although DLTs may occur at any point during treatment, only DLTs occurring during Cycle 1 of treatment in the phase 1 portion will necessarily influence decisions regarding dose-escalation, expansion of a dose level, or evaluation of intermediate dose levels. In the context of emerging clinical data of single-agent MLN9708, dose-escalation of MLN9708 will continue until the MTD has been identified or a maximum planned dose (MPD) is determined to be safe. Based on experience with other drugs in this condition, it is considered unlikely that patients with systemic AL amyloidosis will tolerate doses higher than those tolerated in other diseases, such as multiple myeloma. Therefore, the maximum dose in patients with systemic AL amyloidosis may be the MTD as recommended from the phase 1 single-agent study of weekly MLN9708 in relapsed/refractory multiple myeloma (C16004). For treatment Cycle 2 and beyond, doses of MLN9708 may be held or reduced in an attempt to manage toxicity according to the guidelines outlined in Section 6.6.

More conservative dose-escalation, evaluation of alternative dosing, and expansion of an existing dose level are all permissible following discussions between the sponsor and the investigators, if such measures are needed for patient safety or for a better understanding of the dose-related toxicity, exposure, or pharmacodynamics of MLN9708.

Treatment repeats every 28 days for 3 cycles. If there is no hematologic response (PR, VGPR, or CR) after completion of 3 cycles of single-agent MLN9708, dexamethasone will be added at the initially recommended dose of 40 mg on Days 1 to 4 of every cycle (d1-4 q28days), beginning in Cycle 4. For patients with fluid retention > 3% of body weight despite optimal diuretic therapy, a starting dose of dexamethasone 20 mg should be considered. The patient's response status will be reassessed after 3 additional cycles; if there

is no hematologic response at that time, the patient will be removed from treatment and followed for survival.

If there is response with MLN9708 alone or dexamethasone and MLN9708, the patient may continue on study for up to 12 cycles of treatment in the absence of PD. Study treatment beyond 12 cycles is allowed only if clinical benefit is clearly indicated after a discussion between the Millennium clinician and the investigator treating the patient.

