- Other MLN9708-related nonhematologic toxicities Grade 2 or greater that, in the opinion of the investigator, requires discontinuation of therapy with MLN9708.

[figure not shown]
Patients who do not receive all doses of MLN9708 in Cycle 1 for reasons other than DLTs will be replaced within the cohort. Patients who receive all doses of MLN9708, yet for unforeseen circumstances recovery of toxicity is not available and safety in Cycle 1 cannot be fully evaluated may be replaced within the cohort.

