6.5 Dose-Modification Guidelines

6.5.1 Dose-Modification Guidelines

During the study, the focus of the evaluations is on the assessment of toxicity to document the occurrence of DLT. Although DLTs may occur at any point during treatment, only DLTs occurring during Cycle 1 of treatment must influence decisions regarding dose-escalation, expansion of a dose level, or evaluation of intermediate dose levels. However, DLTs occurring in later cycles may be taken into consideration for dose-escalation decisions, at the discretion of the investigators and sponsors. Unless a DLT is documented to have occurred, no dose modification is allowed during Cycle 1. Dose-limiting toxicities (DLTs) are defined in Section 6.3.1. In the event that a patient experiences DLT during Cycle 1, treatment should be held and the event will be counted toward the assessment of MTD for the given cohort. Patients experiencing DLTs in Cycle 1 may be restarted following recovery from toxicity at the discretion of the investigator according to the guidelines provided in Section

6.5.2 and Section **6.6**. If a decision is made to restart MLN9708 therapy following a DLT, the MLN9708 dose must be reduced 1 dose level.

The patient will be evaluated weekly for possible toxicities that may have occurred after the previous dose(s). Toxicities are to be assessed according to the NCI CTCAE, version 4.03.⁽⁵⁸⁾ Prior to beginning the next cycle of treatment, refer to the guidelines in Sections **6.5.2** and **6.6**. Further clarification can be obtained in consultation with the Millennium clinician (or designee). If multiple toxicities are noted, the dose adjustments and/or delays should be made according to the most severe toxicity guidelines.

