6.6 Criteria for Dose Modification (Delays, Reductions, and Discontinuations)

When possible, toxicities should be attributed to a specific study drug (MLN9708 or dexamethasone [as applicable]) so that dose modifications can be made rationally. If multiple toxicities are noted, the dose adjustments and/or delays should be made once per cycle according to the most severe toxicity guidelines.

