6.6.1 MLN9708 Dose Adjustments for Hematologic Toxicity

Dosage adjustments for hematologic toxicity are outlined in [Table 6-2](#).

Table 6-2 MLN9708 Dose Adjustments for Hematologic Toxicities

Criteria	Action
Within-Cycle Dose Modifications	
If platelet count $\leq 30 \times 10^9/L$ or ANC $\leq 0.75 \times 10^9/L$ on a MLN9708 dosing day (other than Day 1)	MLN9708 dose should be withheld. Complete blood count (CBC) with differential should be repeated at least every other day until the ANC and/or platelet counts have exceeded the prespecified values (see Section 6.5.2.1) on at least 2 occasions. In the event CBC cannot be repeated at least every other day, dose modifications should be made in consultation with sponsor. Upon recovery, MLN9708 may be reinitiated with 1 dose level reduction or by 33% if the patient is receiving the first dose level.
Dose Modifications for Subsequent Treatment Cycles	
Delay of > 2 weeks in the start of a subsequent cycle due to lack of toxicity recovery as defined in Section 6.5.2 :	
 - Hold MLN9708 until resolution as per criteria Section 6.5.2. - Reduce MLN9708 1 dose level or 33% if the patient is receiving the first dose level. - The maximum delay before treatment should be discontinued (except in the case of investigator determined clinical benefit and discussion with the Millennium clinician) will be 3 weeks.
Dose Modifications for Subsequent Treatment Cycles	
All hematologic toxicities	For hematologic toxicity that occurs during a cycle but recover in time for the start of the next cycle, a dose level reduction will be made either based on within-cycle or for

Table 6-2 MLN9708 Dose Adjustments for Hematologic Toxicities

Criteria	Action
	subsequent cycle criteria, but not for both from the same cycle.

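### Protocol 6.5.1 (with 4.1) bars a Cycle 1 hold without a DLT, while Table 6-2 orders one at low counts: state the hold as a Cycle 1 safety exception and align the evaluability rule with it

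*Protocol*

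**What the plan says.** **Dosing in Cycle 1.** Protocol 6.5.1 states: "Unless a DLT is documented to have occurred, no dose modification is allowed during Cycle 1". It ties a Cycle 1 hold to a DLT: "In the event that a patient experiences DLT during Cycle 1, treatment should be held". Section 4.1 agrees: "For treatment Cycle 2 and beyond, doses of MLN9708 may be held or reduced in an attempt to manage toxicity", by the guidelines in Section 6.6. The heading of 6.6 treats a delay as a form of modification: "Criteria for Dose Modification (Delays, Reductions, and Discontinuations".

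The within-cycle row of Table 6-2 (Section 6.6.1) carries no cycle limit. At platelets ≤30 or ANC ≤0.75 × 10⁹/L "on a MLN9708 dosing day (other than Day 1", the "MLN9708 dose should be withheld". It continues: "Upon recovery, MLN9708 may be reinitiated with 1 dose level reduction". Section 6.1 also allows interruptions and dose adjustments for tolerance, again without naming a cycle. Its one Cycle 1 restriction concerns misses due to patient scheduling.

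**Replacement and evaluability.** Section 6.3.1 says: "Patients who do not receive all doses of MLN9708 in Cycle 1 for reasons other than DLTs will be replaced within the cohort". Section 7.9 makes replacement optional for Cycle 1 withdrawals other than for DLT. Protocol 8.1.3 and SAP 2.2 define the DLT-evaluable set, which determines the MTD, as patients who had every Cycle 1 dose or a Cycle 1 DLT. None of these passages separates a miss caused by MLN9708 toxicity from an unrelated one. None says the doses must be at the assigned level, although 8.1.3 asks for full doses without reduction when it defines the PK population.

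**The concern.** A site that reads the dosing table holds the dose; a site that reads 6.5.1 gives it. The same low count on Day 8 or 15 can therefore be handled in opposite ways, in the cycle in which Section 6.8 does not allow growth factors. The first stake is patient safety.

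The second is the count behind a primary endpoint. A patient held for a cytopenia short of a DLT leaves the MTD set and is replaced, just as an unrelated dropout would be. If the patient resumes one level lower, the evaluability wording could be read as a completed, DLT-free course at the assigned level.

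**Working it through.** The plan states no figure on this point, so the check is mainly textual.

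**Step 1: counts that trigger the Table 6-2 hold but are not DLTs under 6.3.1.** Counts are × 10⁹/L, with no clinically significant bleeding, fever or infection.

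| Count on Day 8 or 15 | DLT under 6.3.1? | 6.5.1 with 4.1 | Table 6-2 row |
|---|---|---|---|
| Platelets 25–30 | No | Give dose | Withhold |
| Platelets 10 to <25, under 7 days | No | Give dose | Withhold |
| Platelets <10 | Yes | Hold | Withhold |
| ANC 0.5–0.75 | No | Give dose | Withhold |
| ANC <0.5, under 7 days | No | Give dose | Withhold |

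The Schedule of Events takes hematology on the dosing days, a week apart. A count first found low on Day 8 will usually not yet have a documented 7-day duration, so the duration-based DLTs cannot justify the hold when the decision is made. By comparison, 6.5.2.1 requires platelets ≥75 and ANC ≥1 to start a cycle.

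**Step 2: how wide the gap is.** Most other toxicity-driven misses already become DLTs. Section 6.3.1 covers Grade 3 or higher nonhematologic toxicity (with listed exceptions), related Grade 2 or higher nonhematologic toxicity requiring discontinuation, and a delay of Cycle 2 by more than 2 weeks. What remains is mainly brief or moderate cytopenias.

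**Step 3: what replacement could do to escalation (illustration only).** A 3+3 level escalates on 0/3, or on 1/3 followed by 0/3:

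P(escalate) = (1 − p)³ + 3p(1 − p)⁵.

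Let d be the probability of an observed DLT, o the probability of a toxicity-caused miss short of a DLT, and q the DLT risk those patients would have had at full dose. None of the three is in the documents; all values are assumed. With replacement, p = d/(1 − o). Had those patients been observed at full dose, p = d + oq. Take d = 10%. The last three columns give the current rule minus full-dose observation.

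| o | p, current rule | P(escalate), current rule | q = 0 | q = 0.5 | q = 1 |
|---|---|---|---|---|---|
| 2% | 0.1020 | 0.903 | −0.003 | +0.014 | +0.031 |
| 5% | 0.1053 | 0.897 | −0.009 | +0.035 | +0.084 |
| 10% | 0.1111 | 0.887 | −0.019 | +0.074 | +0.179 |

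Worked line for o = 10%, q = 0.5: full-dose p = 0.10 + 0.05 = 0.15 and P = 0.814, so 0.887 − 0.814 gives +0.074 from unrounded values.

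The sign changes where d/(1 − o) = d + oq, that is at q = d/(1 − o): 10.2%, 10.5% and 11.1%. Below that the current rule is slightly too strict; above it, too lenient. Among up to 30 escalation patients, 30 × o gives 0.6, 1.5 and 3.0 such cases.

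**Step 4: can the documents fix o?** No. Section 1.3 reports no related Grade ≥3 events among 15 patients in C16004 (exact one-sided 95% upper limit 1 − 0.05^(1/15) = 18.1%). The top dose then was 1.68 mg/m², or 2.9 to 3.4 mg at an assumed body surface area of 1.7 to 2.0 m², below the 4.0 mg start here. Section 6.4 adds that 4.0 mg was completed in C16004 without reported DLTs, but that says nothing about cytopenias short of a DLT.

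**The case against.** **The sections can be reconciled.** Section 4.1 places holds under 6.6 at Cycle 2 and beyond. Section 6.5.1 is the rule specific to Cycle 1, and for Cycle 1 toxicity it sends patients to 6.6 only after a DLT. This stands. A reader might infer an unresolvable contradiction; the documents support only an unscoped table row and a loose sentence in 6.1. But the reconciled reading is the one that requires dosing at the counts in Step 1.

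**Patients are already protected.** Section 11.8 permits deviation to remove an immediate hazard, 6.8 allows platelet and red-cell transfusion as indicated, and 6.5.1 offers clarification from the sponsor's clinician. SAP 4 and Protocol 9.1.1 describe ongoing safety review. These reduce the risk. They do not correct the instruction, and a dosing rule should not depend on deviations to be safe.

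**Replacing non-evaluable patients is ordinary 3+3 practice.** This also stands. Replaced patients remain in the Safety population, the RP2D decision in 6.4 weighs Grade 3/4 events and discontinuations, and SAP 5.7.2.2 and 5.10.1.4 report modifications and the events behind them. The cases can be found. No passage, however, requires them to be reviewed before escalation or links them to the DLT count.

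**The reduced-dose reading needs a breach of 6.5.1.** True as the text stands: a Cycle 1 reduction without a DLT is barred. Once the hold is allowed in Cycle 1, the case becomes real and needs a rule.

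**Conclusion.** The point holds as a clarification, minor to moderate in severity and mainly about patient safety. Section 6.5.1 with 4.1 and the Table 6-2 row give opposite instructions for the same Cycle 1 counts, and the reading that reconciles them is the less safe one.

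A reader might go further and infer that replacement makes doses look safer than they are. The documents do not support that. Neither o nor q is given, and the sign depends on whether q lies above or below about 10 to 11%. If 6.5.1 is followed strictly, such misses should be few; at an assumed o = 2% the range is −0.003 to +0.031. The largest value, +0.179, needs o = 10% and every affected patient having a DLT at full dose; at o = 10% and q = 20% the difference is +0.016 (0.887 − 0.871). The comparator, full-dose observation, is also not something the fix would create, so these figures do not measure its benefit.

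**What to change.** 1. In 6.5.1, 4.1 and Table 6-2, state that the hold at platelets ≤30 or ANC ≤0.75 × 10⁹/L applies in Cycle 1, as a safety exception to the rule against modification.
2. Because this makes missed doses short of a DLT more likely, state in 6.3.1, 7.9, 8.1.3 and SAP 2.2 that receiving every Cycle 1 dose means every dose at the assigned level. A patient who misses or takes a reduced Cycle 1 dose for MLN9708-related toxicity short of a DLT is then not counted as a completed non-DLT patient. Replacement follows only after the sponsor and investigators have reviewed the case, before escalation. Unrelated misses are replaced as now. Align the mandatory wording in 6.3.1 with the optional wording in 7.9 at the same time.
3. In SAP 5.10.1.5, list these patients by dose level beside the DLT listing.

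The DLT definition, including its duration limits, and the 3+3 rule do not change. The cost is wording, one listing and a short review for perhaps 0.6 to 3 patients under the assumed rates. The downside is a few more replaced patients and slightly slower escalation.

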6.4 Dose-escalation Rules

The dose intervals will follow the 3+3 traditional escalation rules, starting with the treatment of 3 patients at a planned dose level:

1. If 0 of 3 patients experiences DLT, dose-escalation will proceed to the next higher dose level at which 3 patients will be enrolled.
2. If 1 of 3 patients experiences DLT, 3 more patients will be enrolled at that same dose level.
3. Escalation will continue if 1 of 6 patients experiences DLT.
4. If 2 or more patients in any dose level experience DLT, dosing will stop, and the previous dose level may be considered the MTD or an alternative dose between this dose level and the previous dose level might be further explored.

Figure 6-1 Dose-escalation Algorithm

Planned Dose Levels of MLN9708

The estimated safe starting dose of MLN9708 was selected from the dose-escalation portion of the C16004 study, a phase 1 study of weekly dosing in patients with relapsed and refractory multiple myeloma. The starting dose for Study C16007 was to be either at least 1 dose level below the MTD from Study C16004 if it had been determined and, if not, then a dose level completed without DLTs. The starting dose of 4.0 mg (flat dose) is dose level 2 as seen in [Table 6-1](#). This dose represents a dose completed without reported DLTs in Study C16004 since the MTD has not been determined in that study.

A population PK analysis was performed for MLN9708 to assess the feasibility of switching from BSA-based dosing to flat dosing. A population PK model was built using nonlinear mixed effects modeling in NONMEM VII software compiled with the Intel Fortran 9.2 compiler. Data from both the twice weekly and once weekly IV dosing regimens were used in the analysis (N = 42). Population PK analysis showed that MLN9708 PK can be well described by a 3-compartment model with linear elimination. Race, sex, BSA, and/or body

weight do not appear to significantly affect clearance (CL) and volume of distribution (V_1) in the central compartment. Clearance and volume of distribution in the central compartment are the PK parameters that will affect AUC and C_{max} , respectively. CL and V_1 are primary parameters that are independent of the route of administration of drug. Therefore, BSA is not expected to affect C_{max} or AUC after oral dosing, and thus flat dosing is appropriate for both oral and IV routes of administration.

The planned dose levels of MLN9708 are shown in [Table 6-1](#). The starting dose level in this study is Dose Level 2 (4.0 mg).

Table 6-1 Planned Dose Levels

Dose Level	Dose MLN9708 (mg)
1	3.0
2	4.0
3	5.5
4	7.0
5+	prior dose \times 1.33

Note: More conservative dose-escalation, evaluation of alternative doses, and expansion of an existing dose level are all permissible following discussions between the sponsor and the investigators, if such measures are needed for patient safety or for a better understanding of the dose-related toxicity, exposure, or pharmacodynamics of MLN9708. If emerging data from other MLN9708 phase 1 studies support it, consideration could be given to an alternative dosing schedule, eg, twice weekly, if such a measure is needed to better characterize safety and activity.

Note: The dose levels of MLN9708 shown in this table represent possible estimated doses planned in this study based on those already safely administered to patients treated to date in the C16004 study in which BSA dosing was used.

Based on experience with other drugs for this disease, it is considered unlikely that patients with systemic AL amyloidosis will tolerate doses higher than those tolerated in other diseases, such as multiple myeloma. Therefore, the MTD in patients with systemic AL amyloidosis may be the maximum dose as recommended from the phase 1 single-agent study of weekly MLN9708 in relapsed or refractory multiple myeloma (C16004).

More conservative dose-escalation, evaluation of alternative dosing, and expansion of an existing dose level are all permissible following discussions between the sponsor and the investigators, if such measures are needed for patient safety or for a better understanding of the dose-related toxicity, exposure, or pharmacodynamics of MLN9708. If emerging data from other MLN9708 phase 1 studies support it, consideration could be given to an alternative dosing schedule, eg, twice weekly, if such a measure is needed to better characterize safety and activity.

Recommendation of Phase 2 Dose

The RP2D estimation will be established following evaluation of the available data which will include, but is not limited to, toxicity characterization (Grade 3/4 AEs, SAEs, all grades peripheral neuropathy, and treatment discontinuation) with efficacy (hematologic and organ responses) also taken into consideration. The RP2D will require first cycle DLTs in not more than 0 in 3 or 1 in 6 DLT-evaluable patients enrolled in a single cohort. For the purpose of the RP2D estimation, Cycle 1 data from 6 evaluable patients will be used in addition to the available clinical data supporting tolerance over multiple treatment cycles. AEs that meet DLT criteria in Cycle 2 and beyond will not necessarily influence dose-escalation, but will be considered when determining the RP2D. Toxicities leading to dose modification in Cycle 2 and beyond will not necessarily influence dose-escalation, but will be considered when determining the RP2D.

Once the MTD/RP2D has been established, 2 expansion cohorts of patients with relapsed or refractory amyloidosis, including approximately 10 proteasome inhibitor-naïve patients and approximately 16 proteasome inhibitor-exposed patients, will be treated at the MTD/RP2D to more fully characterize the safety, tolerability, and efficacy of MLN9708, and the PK and pharmacodynamics of MLN9708 in this patient population. As many as 30 patients will be enrolled in the dose-escalation portion of the study, and as many as 20 additional patients (26 in total, including 6 patients from the dose-escalation portion) will be enrolled in the expansion cohorts.

6.5 Dose-Modification Guidelines

6.5.1 Dose-Modification Guidelines

During the study, the focus of the evaluations is on the assessment of toxicity to document the occurrence of DLT. Although DLTs may occur at any point during treatment, only DLTs occurring during Cycle 1 of treatment must influence decisions regarding dose-escalation, expansion of a dose level, or evaluation of intermediate dose levels. However, DLTs occurring in later cycles may be taken into consideration for dose-escalation decisions, at the discretion of the investigators and sponsors. Unless a DLT is documented to have occurred, no dose modification is allowed during Cycle 1. Dose-limiting toxicities (DLTs) are defined in Section 6.3.1. In the event that a patient experiences DLT during Cycle 1, treatment should be held and the event will be counted toward the assessment of MTD for the given cohort. Patients experiencing DLTs in Cycle 1 may be restarted following recovery from toxicity at the discretion of the investigator according to the guidelines provided in Section

6.5.2 and Section **6.6**. If a decision is made to restart MLN9708 therapy following a DLT, the MLN9708 dose must be reduced 1 dose level.

The patient will be evaluated weekly for possible toxicities that may have occurred after the previous dose(s). Toxicities are to be assessed according to the NCI CTCAE, version 4.03.⁽⁵⁸⁾ Prior to beginning the next cycle of treatment, refer to the guidelines in Sections **6.5.2** and **6.6**. Further clarification can be obtained in consultation with the Millennium clinician (or designee). If multiple toxicities are noted, the dose adjustments and/or delays should be made according to the most severe toxicity guidelines.

6.5.2 Criteria for Toxicity Recovery Before Beginning the Next Cycle of Treatment

If a patient fails to meet the criteria outlined in the following sections for beginning the next cycle of treatment, initiation of the next cycle should be delayed for 1 week. At the end of that time, the patient should be re-evaluated to determine whether the criteria for retreatment have been met. If the start of the next cycle needs to be delayed for more than 2 weeks due to incomplete recovery from treatment-related toxicity, refer to the recommended dose modification guidelines provided in Section **6.6**. The maximum delay before treatment should be discontinued will be 3 weeks (except in the case of investigator determined clinical benefit and discussion with the Millennium clinician).

NOTE: A delay of more than 2 weeks because of lack of adequate recovery of MLN9708-related hematologic or nonhematologic toxicities occurring during Cycle 1 meets the criteria for a DLT in the given cohort (refer to Section **6.3**). If the patient is to receive additional treatment despite a DLT, the dose of MLN9708 will be reduced by at least 1 dose level (or by 33% if the patient is receiving the first dose level) upon resolution of toxicity (refer to Section **6.6**).

